9.2.4 Secondary Efficacy Analysis: Clinical Outcomes

Each clinical outcome and type of decompensation event will be summarized descriptively by treatment group. This descriptive summary will summarize subjects and events across the entire study period (i.e., all post-baseline data collected up through Month 24). This summary will also be provided for all post-baseline data collected through Month 12.

9.2.5 Secondary Efficacy Analysis: Biomarkers

Biomarker endpoints will be summarized descriptively at each visit by treatment group. Change from baseline values for each biomarker at each post-baseline visit will be summarized descriptively by treatment group. If log-transformations are applied to any of the biomarker endpoints, the geometric mean, coefficient of variation, and percent relative change will also be included in the descriptive statistics.

9.2.6 Secondary Efficacy Analysis: Fibrosis Improvement: NASH CRN

The primary efficacy analysis will be repeated using the mapping from the Ishak Fibrosis Scoring System to evaluate the proportion of subjects who have at least at one-point improvement in fibrosis based on the mapping to this scoring system at Month 12 and Month 24.

9.2.7 Secondary Efficacy Analysis: Liver Stiffness

Liver stiffness will be summarized descriptively at each visit collected by treatment group. Change from baseline values in liver stiffness at each post-baseline visit will also be summarized descriptively by treatment group.

9.3 EXPLORATORY EFFICACY ANALYSES

The percent collagen and percent SMA from morphometric analysis will be summarized descriptively at Month 12 and Month 24 by treatment group. Change from baseline values in percent collagen and SMA will be summarized descriptively by treatment group and overall.

9.4 EXAMINATION OF SUBGROUPS FOR EFFICACY ENDPOINTS

The primary endpoint will be summarized descriptively using observed cases by treatment group for the following subgroups:

- Gender (Female, Male)
- Time since transplant (\leq median, $>$ median)
- Time since SVR (\leq median, $>$ median)
- Baseline Ishak fibrosis score strata (F2, F3-F5, F6)
- Baseline Ishak fibrosis score grouping A (F2-F3, F4-F6)
- Baseline Ishak fibrosis score grouping B (F2-F3, F3-F4, F5-F6)
- Baseline Ishak fibrosis score (F2, F3, F4, F5, F6)
- Investigative site

No statistical hypothesis testing will be conducted for these subgroup analyses.

10 PHARMACOKINETIC (PK) ANALYSES

All concentration levels and collection times for emricasan and its metabolites from the Month 1 visit will be provided in a listing. Population PK concentrations will be provided in a listing by visit.

10.1 EMRICASAN, METABOLITES, AND IMMUNOSUPPRESSION PK PROFILES

Blood samples will be collected at the Month 1 visit for generation of PK profiles for emricasan (IDN-6556), three metabolites (IDN-8741, IDN-6556-6, and IDN-6556-9), and four immunosuppressants (cyclosporine, everolimus, mycophenolate, and tacrolimus). The concentration levels will be used to derive the PK parameters that will be included in the PK analysis. These analyses will be conducted outside the scope of this SAP with a separate PK report being generated for inclusion in the clinical study report as an appendix.

10.2 POPULATION PK ANALYSIS

Blood samples will be collected for population PK assessment. A population analysis of time versus emricasan plasma concentration data will be performed using the nonlinear mixed effects modeling approach. The software NONMEM (UCSF, California, USA) will be used to derive the population mean and variance values for specific PK parameters. Additionally, a relationship between PK parameters (or dose) and efficacy, as well as AEs, will be investigated.

In the PK (and pharmacodynamics, PD) analysis, several covariates will be tested and incorporated into the structural model if shown to significantly improve the model's ability to describe the data. The final PK/PD model for emricasan will be obtained from this "full" model using only the covariate relationships that are thought to result in clinically significant alterations in drug PK and/or PD. This model will include data from this study and also from previously conducted emricasan studies.

Results from these population PK/PD models will be provided in a separate report and all analyses are outside the scope of this SAP.

11 SAFETY ANALYSES

All safety endpoints will be provided in listings by unique subject number and visit. All Safety related tables will be produced using the Safety Set.

11.1 DOSING AND EXTENT OF EXPOSURE

Study drug capsule counts will be summarized descriptively by treatment group and visit. Treatment compliance and extent of treatment exposure endpoints (i.e., days and person years of exposure) will be summarized descriptively by treatment group.

11.2 ADVERSE EVENTS

The incidence of TEAEs will be summarized descriptively by treatment group for the following:

- system organ class (SOC) and preferred term
- SOC, preferred term, and severity
- SOC and preferred term for TEAEs classified as related to study drug
- SOC and preferred term for events having incidence of $\geq 5\%$ in any treatment group
- SOC and preferred term for subjects with study discontinuation due to the AE
- SOC and preferred term for subjects with study drug interruption due to the AE
- preferred term (alphabetical and highest incidence in all emricasan dose groups)

Missing values for severity, relationship to study drug, action taken with study drug, treatment required, and/or outcome will be summarized as unknown.

The incidence of SAEs for each SAE will be summarized descriptively by treatment group and overall for the following:

- SOC and preferred term
- SOC, preferred term, and severity
- SOC and preferred term for SAEs classified as related to study drug
- preferred term (alphabetical and highest incidence in all emricasan dose groups)

Subject listings by unique subject number and visit will be provided for the listings below:

- All AEs
- Subjects who discontinued from the study
- Subjects who had a study drug interruption
- Subjects with SAEs
- Subjects who died

11.3 LIVER ULTRASOUND

Incidence of abnormal findings and number of events from the liver ultrasound will be summarized by treatment group. This summary will also include the incidence and events

considered to be clinically significant. The list of abnormal events, as determined by a blinded medical review prior to database lock, will also be provided.

11.4 POTENTIAL LIVER INJURY

Subject incidence of the categorizations for ALT, AST, and total bilirubin as described in [Section 5.4.5](#) will be summarized descriptively by treatment group and visit. An evaluation of drug-induced serious hepatotoxicity (eDISH) plot of all subjects coded by treatment group will be provided, which displays the ALT or AST value (on a log 10 scale) versus the total bilirubin value (on a log 10 scale). The eDISH plot will be produced with concurrent results for ALT, AST, and bilirubin by visit and an additional plot that displays the maximum post-baseline values of ALT, AST and total bilirubin (both on a log 10 scale).

11.5 LABORATORY MEASUREMENTS

Hematology, chemistry, coagulation, and alpha-fetoprotein laboratory parameters will be summarized descriptively at each visit by treatment group. Where applicable, change from baseline in laboratory tests will also be summarized descriptively at each post-baseline visit by treatment group.

A shift table will be provided for descriptively summarizing the classification around the normal range of each hematology, chemistry, coagulation, and alpha-fetoprotein laboratory parameter between baseline to each of the minimum and maximum post-baseline values.

An additional shift table will be provided for descriptively summarizing the classification of urinalysis laboratory parameters between baseline and the maximum post-baseline values by treatment group and overall.

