7.1 Inclusion Criteria

To participate in this study, subjects must meet **all** of the following criteria:

1. Male or female subjects of minimum adult legal age (according to local laws for signing the informed consent document), able to provide written informed consent, and able to understand and willing to comply with the requirements of the study
2. History of orthotopic liver transplantation for HCV-induced liver disease
Note: Living donor or cadaveric transplantation will be permitted into the study. HCV positive donor livers will also be permitted into the study.
3. Diagnosis of HCV infection (HCV-RNA detectable in serum) and liver fibrosis or cirrhosis status post liver transplantation, and achieved a sustained virologic response (SVR) with anti-viral HCV treatment within 18 months of Day 1
Note: For the purposes of this study, subjects must meet the definition of SVR as defined by the anti-HCV regimen used.
4. Liver fibrosis or cirrhosis on liver histology as read by central histopathologist of Ishak F2 to F6 within three months of Day 1
Note: Baseline liver histology in close approximation of the three month window may be permitted on a case by case basis after discussion with the Medical Monitor.
5. Available liver tissue for central read (ten, 4-microns-thick, unstained liver sections)
6. Willing to undergo protocol-determined liver biopsies during the study
7. Hemoglobin ≥ 11 g/dL, platelet count $\geq 75 \times 10^9/L$, WBC $\geq 2.0 \times 10^9/L$
Note: As these parameters may be influenced by immunosuppressive therapy, small variances may be permitted on a case by case basis after discussion with the Medical Monitor.
8. On stable doses of immunosuppressant therapy for ≥ 3 months prior to Day 1
9. Willingness to utilize two reliable forms of contraception (for both males and females of childbearing potential) from Screening to one month after the last dose of study drug

Title: A Multicenter, Double-Blind, Randomized Trial of IDN-6556 in Subjects Who had Hepatitis C Virus (HCV) Reinfection and Liver Fibrosis or Cirrhosis following Orthotopic Liver Transplantation for Chronic HCV Infection and Who Subsequently Achieved a Sustained Virologic Response Following anti-HCV Therapy

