7.2 Exclusion Criteria

Subjects who meet **any** of the following criteria will be excluded from the study:

1. Known active infection with hepatitis B virus (HBV) and/or human immunodeficiency virus (HIV)
2. History of renal transplant and/or severe renal impairment defined as eGFR (estimated glomerular filtration rate) of less than 30 mL/min/1.73 m²
3. Subjects with post-transplant liver fibrosis of any etiology other than chronic HCV infection
4. History of autoimmune hepatitis
5. History of autoimmune cholestatic disease
6. Wilson's disease, defined by ceruloplasmin below the limits of normal and liver histology consistent with Wilson's disease
7. Alpha-1-antitrypsin deficiency defined by serum alpha-1-antitrypsin level less than normal and liver histology consistent with alpha-1-antitrypsin deficiency
8. Hemochromatosis or secondary iron overload as defined by the following:
 - a. Presence of 3+ or 4+ iron on liver biopsy stain or a history of previous phlebotomy for iron overload, or
 - b. Iron saturation (serum iron/IBCx100%) of greater than 50%
9. Subjects with diagnosed or suspected systemic lupus erythematosus (SLE) and/or rheumatoid arthritis (RA)
10. Drug induced liver disease defined on the basis of typical exposure and history of ingestion of drugs known to produce hepatic injury (including but not limited to high dose estrogens, tetracycline or amiodarone) in the previous six months
11. Cholestatic liver disease
12. Inflammatory bowel disease
13. Bile duct obstruction as shown by imaging studies
14. Alpha-fetoprotein levels > 200 ng/mL
15. Evidence of tumor burden > Milan criteria, or evidence of micro- or macrovascular invasion in explanted liver
16. Hepatocellular carcinoma (HCC) at entry into the study
17. Subjects with active or history of non-liver malignancies other than curatively treated skin cancer (basal cell or squamous cell carcinomas)
18. History of alcohol abuse within the last year
19. History of pancreatitis
20. Concurrent sirolimus (rapamycin) use
21. Evidence of rejection of implanted liver within three months of Day 1, unless adequately treated and resolved prior to Day 1
22. Any drugs known to cause fibrosis, with the exception of immunosuppressive therapy, six months prior to dosing and throughout the study

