12.6.2 Safety Analysis

Safety will be assessed by adverse events, laboratory tests, vital signs, physical examinations, ECGs, and liver and abdominal ultrasounds.

Adverse events will be tabulated by body system and preferred term. The number of entries, as well as the number of subjects will be reported. The nature, intensity, frequency, and relationship to IDN-6556 or placebo of adverse events will be described for all study subjects.

Results of laboratory tests, vital signs, physical examinations, and ECGs will be analyzed descriptively. Abnormal laboratory and ECG findings will be tabulated against appropriate cut-off points (e.g., $\geq 2 \times$ ULN) using frequency counts and percentages.

Furthermore, any prior and concomitant medication will be described.

Graphical presentation of results will be performed, where appropriate.

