***Hepatic Encephalopathy grading:**

- Grade 0: normal consciousness, personality, neurological examination, electroencephalogram
- Grade 1: restless, sleep disturbed, irritable/agitated, tremor, impaired handwriting, 5 cps waves
- Grade 2: lethargic, time-disorientated, inappropriate, asterixis, ataxia, slow triphasic waves
- Grade 3: somnolent, stuporous, place-disoriented, hyperactive reflexes, rigidity, slower waves
- Grade 4: unrousable coma, no personality/behavior, decerebrate, slow 2-3 cps delta activity

Determination of Encephalopathy for the Calculation of the Child-Pugh Score

Encephalopathy Test (If needed)

The number connection test will facilitate the diagnosis of hepatic encephalopathy. The test should be performed by the subject after the investigator's verbal instructions. The purpose is to correctly combine numbers with a pencil on a test chart as fast as possible. If the subject needs more than 40 seconds to perform the task, there is a strong indication of a latent hepatic encephalopathy.

Title: A Multicenter, Double-Blind, Randomized Trial of IDN-6556 in Subjects Who had Hepatitis C Virus (HCV) Reinfection and Liver Fibrosis or Cirrhosis following Orthotopic Liver Transplantation for Chronic HCV Infection and Who Subsequently Achieved a Sustained Virologic Response Following anti-HCV Therapy

Table III.2 Classification of Renal Function Based on GFR (eGFR) or Estimated Creatinine Clearance (CLcr)^a

| Stage | Description ^b | eGFR ^c (mL/min/1.73m ²) | CLcr ^d (mL/min) |
|-------|--------------------------------|---|-------------------------------|
| 1 | Control (normal) GFR | ≥ 90 | ≥ 90 |
| 2 | Mild decrease in GFR | 60 - 89 | 60 - 89 |
| 3 | Moderate decrease in GFR | 30-59 | 30 - 59 |
| 4 | Severe decrease in GFR | 15 - 29 | 15 - 29 |
| 5 | End Stage Renal Disease (ESRD) | <15 not on dialysis | <15 not on dialysis |
| | | Requiring dialysis | Requiring dialysis |

- a. In some situations, collection of 24-hour urine samples for measurement of creatinine clearance, or measurement of clearance of an exogenous filtration marker, may provide better estimates of GFR than the prediction equations. The situations include determination of GFR for patients in the following scenarios: undergoing kidney replacement therapy; acute renal failure; extremes of age, body size, or muscle mass; conditions of severe malnutrition or obesity; disease of skeletal muscle; or on a vegetarian diet.

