5.4.6 Laboratory Measurements

Laboratory tests include measurements across panels of hematology, coagulation, chemistry, and urinalysis. In addition, alpha-fetoprotein is measured at screening and every 6 months during the study. All specific laboratory tests are listed in detail in clinical protocol [IDN-6556-07](#). Normal ranges, where applicable, will be provided by the central laboratory and used to identify laboratory measurements outside the normal range.

Changes from baseline will be derived for each continuous laboratory parameter. Laboratory tests with categorical results will have no derivations made.

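### Apart from ALT, AST and total bilirubin, the SAP gives laboratory tests no cut-off counts although the protocol promises them, and its normal-range shift table cannot show further worsening in subjects already abnormal at baseline

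*SAP*

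**What the plan says.** Protocol 12.6.2 (Safety Analysis) states: "Abnormal laboratory and ECG findings will be tabulated against appropriate cut-off points". The results are to be given as counts and percentages. The one example is at least 2 × ULN, and no parameters are named.

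The SAP sets cut-off categories in two places:

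- ALT, AST and total bilirubin. SAP 5.4.5 defines bands in multiples of ULN, values above 2 and 3 times baseline, and combined transaminase and bilirubin criteria. SAP 11.4 reports them by arm and visit, with eDISH plots.
- QTcB and QTcF. SAP 5.4.8 and 11.7 use limits of 450, 480 and 500 ms, and changes of 30 and 60 ms.

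For hematology, chemistry, coagulation and AFP, SAP 11.5 gives values by visit, change from baseline by visit, and a shift table: "A shift table will be provided for descriptively summarizing the classification around the normal range of each hematology, chemistry, coagulation, and alpha-fetoprotein laboratory parameter". The shift runs from baseline to the minimum and to the maximum post-baseline value. The ranges come from the central laboratory and are "used to identify laboratory measurements outside the normal range" (SAP 5.4.6). Their numerical limits are not in the documents.

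On entry, Protocol 7.2 excludes "Alpha-fetoprotein levels > 200 ng/mL" and "severe renal impairment defined as eGFR (estimated glomerular filtration rate) of less than 30 mL/min/1.73 m²". Protocol 7.1 asks for platelets of at least 75 and white cells of at least 2.0 (both × 10^9/L), then adds: "As these parameters may be influenced by immunosuppressive therapy, small variances may be permitted", case by case.

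SAP 14.1 lists changes to the primary endpoint and analysis, the use of observed cases, and local biopsies. It describes everything else as elaboration of the protocol. SAP 14.2 adds one laboratory change, the new baseline definition. Neither mentions laboratory cut-offs.

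**The concern.** A normal-range shift table suits subjects who start inside the range. Here the entry criteria admit values that are plausibly outside it, so the one worst-value table for these tests is blind to further deterioration in those subjects. The protocol's cut-off tabulation would have covered this, but the SAP carries it out for three liver tests only and does not record the narrowing.

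The tests concerned bear on risks that the protocol itself raises: hepatocellular carcinoma in cirrhosis (4.1), with F6 subjects eligible, and malignancy under long-term immunosuppression (8.1.2). AFP is measured every six months, and a sustained rise in it forms part of one criterion for an additional biopsy (8.1.1). Safety and tolerability is a stated secondary objective. What is at stake is whether the report can say, by arm, how many subjects had a marked change in these tests.

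**Working it through.** The plan states no figure to reproduce. The check is on what the table can show.

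**Rule.** Classify a value v as low if v < LLN (lower limit of normal), high if v > ULN, and normal otherwise. This is the natural reading of a classification around the normal range with shifts to both minimum and maximum. If the baseline b is below LLN and the worst value m is below b, then m < b < LLN and the cell is low to low, whatever the size of b − m. The same holds above ULN.

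**Inputs.** Baselines are values that Protocol 7.1 and 7.2 admit. Post-baseline values are illustrative. Laboratory limits are assumed and varied, because the documents give none.

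| Test | Baseline → worst | Assumed limit | Cell |
|---|---|---|---|
| Platelets (× 10^9/L) | 75 → 20 | LLN 130, 140, 150 | low → low for all |
| Platelets (× 10^9/L) | 120 → 20 | LLN 130, 140, 150 | low → low for all |
| White cells (× 10^9/L) | 2.0 → 0.5 | LLN 3.5, 4.0, 4.5 | low → low for all |
| AFP (ng/mL) | 20 → 1000 | ULN 6, 8, 10, 15 | high → high for all |
| AFP (ng/mL) | 200 → 2000 | ULN 6, 8, 10, 15 | high → high for all |
| AFP (ng/mL) | 5 → 1000 | ULN 6, 8, 10, 15 | normal → high for all |

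The first five rows register no shift. The last one does, so the limitation is confined to subjects who start outside the range and worsen in the same direction.

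**Renal function.** The protocol's own Table III.2 (Appendix III) puts "Control (normal) GFR" at 90 or more, for both eGFR and estimated creatinine clearance. Entry is allowed from eGFR 30, so subjects at 30 to 89 can enter below that table's normal category. Whether their serum creatinine exceeds the laboratory's ULN is not given. If it does, any further rise stays high to high.

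**What the other outputs show.** SAP 7 includes minimum and maximum in continuous summaries. Suppose a subject's platelets fall from 100 to 20 at a summarized visit. The change is 20 − 100 = −80, so that arm's minimum at the visit is 20 or lower and its minimum change is −80 or lower. With the planned arms of 40 and 20, this one subject moves the mean change by −80/40 = −2 on active or −80/20 = −4 on placebo. The minimum reveals that a large fall occurred. It does not reveal how many: one such subject in 40 (2.5%) and five in 40 (12.5%) can leave the same minimum.

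**The case against.** The strongest reply has four parts.

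- The protocol speaks of appropriate cut-offs and names no parameter. The SAP meets this for the liver tests in more detail than the protocol's example, and for QTc. Protocol 12.1 also lets the SAP modify the plan. This stands: a reader might infer that the cut-off tables were abandoned, and they were not. What remains is that other laboratory tests have none and SAP 14 does not say so, although it does record the change of laboratory baseline.
- Large changes are not hidden. They appear in minima and maxima by visit, and in listings by subject (SAP 11). This stands, but neither is the count and percentage that Protocol 12.6.2 promises.
- The risks have other routes. Ultrasound is reviewed for new focal lesions and tabulated by arm (SAP 5.4.4, 11.3). Laboratory abnormalities judged clinically significant become adverse events (Protocol 13.2.3), which are tabulated by arm. The DMC reviews safety data every six months (SAP 13). This stands too, so the documents do not support an inference that the safety analysis as a whole would miss the harm. The adverse-event route does depend on the investigator's judgement, so a large change may never become an event.
- Shift tables with continuous summaries are a conventional descriptive package for a 60-subject Phase 2 trial, and no decision rule depends on them. That is fair and limits the weight of the point.

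SAP 7 also defines a baseline for laboratory abnormality summaries, which might suggest that a further table is intended. No section specifies one beyond the shift tables and the liver categories.

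**Conclusion.** The point holds in a limited form. For laboratory tests other than ALT, AST and total bilirubin, the SAP omits the cut-off counts that Protocol 12.6.2 promises, and does not declare it. The shift table in their place cannot register same-direction worsening in a subject already abnormal at baseline; for such a subject this is a property of the table and needs no assumption.

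That entry admits such subjects rests on assumed laboratory limits for AFP, platelets and white cells. For renal function it is supported by the protocol's own Table III.2. A reader might infer that much of the trial population is affected. The documents do not support any number: entry limits are bounds, not distributions, and the share abnormal at baseline will differ by test.

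The consequence is a missing count by arm, not concealed data. The primary endpoint and the decision guideline are unaffected. This is a low-cost improvement to safety reporting.

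**What to change.** In SAP 11.5, add one descriptive table by arm for key tests, for example AFP, creatinine, platelets, white cells or neutrophils, hemoglobin and INR. For each test, count the subjects whose worst post-baseline value crosses prespecified multiples of ULN or of baseline, or falls in graded bands that extend beyond the entry limit. The protocol's example of at least 2 × ULN, and the multiples of baseline in SAP 5.4.5, offer a ready pattern for tests where a rise is the concern; falls need bands on the low side. State which baseline applies: SAP 7 already assigns the last value up to Day 1 to abnormality summaries.

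Record the table in SAP 14. If the sponsor prefers not to add it, SAP 14 should at least declare that cut-off tabulation is limited to ALT, AST, total bilirubin and QTc.

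These are reporting categories only and set no rule for treating or withdrawing a subject. The cost is a little SAP wording and programming, and one extra table from central-laboratory data already held.
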